## 14. REFERENCES

### EXAMPLE APPENDICES

#### APPENDIX 1.

#### **GLOSSARY OF ABBREVIATIONS**

AE	Adverse Event
AR	Adverse Reaction
ASR	Annual Safety Report
CA	Competent Authority
CI	Chief Investigator
CRF	Case Report Form
CRO	Contract Research Organisation
CTA	Clinical Trial Authorisation
DMC	Data Monitoring Committee
GAFREC	Governance Arrangements for NHS Research Ethics
GCP	Good Clinical Practice
ICF	Informed Consent Form
Main REC	Main Research Ethics Committee
NHS R&D	National Health Service Research & Development
PI	Principal Investigator
PIS	Patient Information Sheet
QA	Quality Assurance
QC	Quality Control
RCT	Randomised Control Trial
REC	Research Ethics Committee
SAR	Serious Adverse Reaction
SAE	Serious Adverse Event
SDV	Source Document Verification
SOP	Standard Operating Procedure
TMG	Trial Management Group

#### **KEYWORDS**

Inflammation, infection, preschool wheeze, phenotype, inhaled steroids, antibiotics, eosinophils, clinical guidelines

## STUDY SUMMARY

**TITLE:** Use of pathological phenotype to determine optimal management for moderate to severe preschool wheeze

**SHORT TITLE:** Preschool wheeze: Inflammation/Infection Guided Management (PrIGMa)

**RATIONALE:** At least one-third of all children under 5 years suffer from wheezing and breathlessness, but despite the high incidence, there are few effective therapies. Current guidelines recommend the management of preschool wheezing should be determined by clinical phenotype. However, this is based predominantly on expert consensus with little evidence. The current guidelines have not been compared to other strategies. Current management does not take account of objective evidence of underlying inflammation or infection, however there is evidence to support that preschool wheezers have pathologically distinct phenotypes. This study will therefore determine the efficacy of treating preschool wheeze based on objective biomarkers of inflammation and presence of bacterial infection, and compare this to current clinical guidelines based management. This is a novel approach to managing preschool wheeze, which if effective, will have a significant impact on changing current clinical practice, and can be instituted within 5 years.

**AIMS:** To compare management of preschool wheeze using current clinical guidelines to management determined by eosinophilic inflammation in sputum or blood, and infection in sputum or oropharyngeal swabs

To determine numbers that would be needed to perform a large, multi-centre randomised trial comparing management according pathological phenotype to current clinical guidelines

**DESIGN:** Randomised, single blind, controlled trial comparing management of preschool wheeze based on inflammation and infection profile to current standard of care – the intervention will be over a 4 month period. This is a proof of concept study to determine feasibility of this approach and to obtain data to allow an assessment of numbers that would be needed for a larger randomised trial.

Subjects will be recruited from out-patient clinics and attend for a screening / research visit during which assessments of pathological phenotype (bacterial infection and inflammation) will be made from induced sputum and blood. Their clinical phenotype will be determined by the Consultant. Subsequently, patients will be randomised to one of two arms:

- i) current clinical care (as directed by their Consultant)
- ii) pathological phenotype based management – presence of eosinophilia in blood ( $>32\%$ ) or induced sputum ( $>2.4\%$ ) – will receive twice daily inhaled steroids (beclomethasone 200mcg bd) for 4 months, presence of bacterial infection in

induced sputum or oropharyngeal swab – will receive 4 weeks of antibiotics targeted to the isolate, IF BOTH eosinophilic inflammation AND infection are present, then inflammation alone will be treated for 4 months.

All patients will continue on as required bronchodilator therapy, and any other anti-inflammatory therapy (other than inhaled steroids) e.g. montelukast.

**OUTCOME MEASURES:**

**Primary outcome** – number of unscheduled healthcare visits (UHCV) during the 4 month intervention period

**Secondary outcomes** – health related quality of life, number of hospital admissions, number of days of oral steroids during the 4 month intervention period, and up to 1 year later

**POPULATION:** Preschool children, aged 1-5 years attending out-patient clinic for recurrent wheezing

**ELIGIBILITY:**

Age 1-5 years

≥ 2 courses of oral steroids (steroid bursts) OR hospital admissions in the last 12 months for acute wheezing, at least one of which is in the last 6 months

**TREATMENT:**

1. Inflammation / infection based management (pathological phenotype based management):

– use induced sputum and blood eosinophil count to determine whether regular inhaled steroids are prescribed for 4 months, or antibiotics are prescribed for 4 weeks (if sputum has a positive bacterial growth), if BOTH eosinophilic inflammation and bacterial infection are present, then treat the inflammation alone for 4 months

2. Current standard of care:

[figure not shown]
- Treat for 4 months as directed by the child's clinician – according to current clinical guidelines

**DURATION:**

Duration of intervention: 4 months

Duration of follow-up: after 4 months, then 6 monthly until the end of the trial.

## REFERENCE DIAGRAM OF TRIAL DESIGN:

## 1. INTRODUCTION

### 1.1 BACKGROUND

At least one-third of all children under 5 years suffer from wheezing and breathlessness, but despite the high incidence, there are few effective therapies. Current guidelines recommend the management of preschool wheezing should be determined by clinical phenotype. However, this is based predominantly on expert consensus with little evidence. The two clinical phenotypes are episodic wheeze, in which wheeze occurs during discrete episodes, usually in association with an upper respiratory tract infection, with no symptoms in between, and multiple trigger wheezing, with discrete episodes and symptoms in between. The current approach has several limitations: i) It relies on accurate parental reporting of symptom pattern, which may not always be clearly distinguishable as episodic or multiple trigger. ii) Clinical phenotypes may switch within patients in a short period, such as only 3 months. iii) The underlying infectious cause of acute episodes is not considered. Although it was previously thought that most episodes are precipitated by viral infections, it is now recognised that an equal number are also caused by bacterial infection. The current guidelines have not been compared to other strategies. It is essential that the correct approach is adopted since therapeutic options include steroids, which if administered incorrectly result in adverse effects, the most worrying in the preschool age-group being reduced growth.

### Evidence to support pathologically distinct preschool wheeze phenotypes

The pathology of allergic asthma in adults and school-aged children is characterised by airway eosinophilic inflammation and structural airway wall changes, termed airway remodelling. Eosinophilia is usually steroid sensitive and thus the mainstay of therapy includes regular inhaled steroids. It is assumed that the preschool multiple trigger wheeze phenotype resembles allergic asthma and therefore is responsive to steroid therapy, whilst episodic wheeze is pathologically distinct and so is steroid unresponsive. Preschool wheezers have been shown to have bronchial eosinophilia(8:9). Furthermore, we have shown that most episodic wheezers do not have eosinophilia, and pathologically resemble non-wheezing controls. Levels of exhaled nitric oxide (a non-invasive marker of airway inflammation) are more likely to be elevated in multiple trigger wheezers. Lung function assessments also suggest multiple trigger wheezers have increased airway resistance and are distinct to episodic wheezers who have relatively normal lung function similar to controls. Despite this evidence supporting pathophysiologically distinct phenotypes, preschool wheeze is still treated using clinical symptom patterns, without the additional use of inflammatory biomarkers to guide therapy. Importantly, data from adults with moderate asthma suggests use of inflammation guided therapy is superior in reducing exacerbations compared to clinical guidelines based therapy. But, in children with severe asthma, the same approach was not

beneficial, suggesting the benefits of inflammation guided therapy may be influenced by disease severity.

The lower airway is not sterile and its microbial composition is altered in children with asthma, but this can only be detected using molecular biology techniques such as 16SPCR. Airway microbial composition in preschool children is unknown. However, it is established that a significant proportion of recurrent preschool wheezers have airway bacterial infection identified using traditional culture techniques. An important unanswered question is the relevance of the microbial flora in determining recurrent wheezing in preschool children.

## 1.2 Rationale for Current study

### Clinical Impact and Relevance

Wheezing and breathlessness in preschool children is common, but difficult to treat, and results in exacerbations requiring frequent healthcare visits. Of all UK admissions for children aged 1-16 years with acute wheeze or asthma between 1998-2005, approximately 75% of admissions each year were for children under 5 years old (median age 3 years), and the rate did not change over the seven year period. In addition, caring for preschool children with wheeze cost the healthcare service an estimated £53 million in 1998/99, with the majority of costs being attributable to inpatient stays. The costs to families caring for an unwell child at home or in hospital was between £10-40 per day, this was in addition to the costs of taking unforeseen time off work. Current management of preschool wheeze is based on clinical phenotype alone and does not take account of objective evidence of underlying inflammation or infection. Given the drawbacks of parental recall bias, clinical phenotype switching and adverse effects of steroid therapy if used inappropriately, and the available evidence for pathologically distinct phenotypes in preschool wheezers, this study will determine the efficacy of treating preschool wheeze based on objective biomarkers of inflammation and presence of bacterial infection, and compare this to current clinical guidelines based management. This is a novel approach to managing preschool wheeze, which if effective, will have a significant impact on changing current clinical practice, and can be instituted within 5 years.

Since preschool wheezing is predominantly characterised by frequent exacerbations and a sub-group of wheezers have evidence of eosinophilia (elevated exhaled nitric oxide, increased airway eosinophils), while others are likely to have evidence of airway bacterial infection, management based on objective evidence of inflammatory and infectious phenotype, rather than symptom pattern and clinical phenotype is an approach that warrants investigation. Importantly, the impact of disease severity and the optimal samples upon which to guide therapy also need investigation.

### Hypothesis

Targeted treatment of preschool wheeze determined by airway inflammation and infection will result in better outcomes including fewer unscheduled healthcare visits, improved health related quality of life (HRQOL) for the child and family, and fewer days of oral steroid therapy compared to using current clinical guidelines.

## **2. STUDY OBJECTIVES**

1. Compare treatment of recurrent wheezing in preschool children aged 1-5years with  $\geq 2$  courses of oral steroids for acute wheeze in the previous 12 months (at least 1 course in the previous 6 months) based on evidence of eosinophilic inflammation (blood or sputum eosinophils) and bacterial infection (oropharyngeal swabs) to current clinical guidelines.
2. Compare treatment efficacy of this approach in recurrent severe wheezers (those undergoing a clinically indicated bronchoscopy for severe symptoms) to moderate wheezers (those not undergoing bronchoscopy).

## **3. STUDY DESIGN**

This is a single blind, randomised, controlled trial comparing management of moderate to severe preschool wheeze according to current clinical guidelines to management determined by inflammation and infection profile (pathological phenotype).

**Study duration:** The intervention phase of the study will last for 4 months, with follow-up immediately after the intervention period and 6 monthly thereafter until the end of the trial. The minimum follow-up is at the end of the 4 month intervention period, maximum follow-up will be for 3 years. During the 4 month intervention period, families will be contacted weekly by phone call for an update on unscheduled healthcare visits and symptoms.

**Type of subjects to be recruited:** All subjects will be aged between 1 and 5 years old. All subjects will have moderate to severe preschool wheeze, defined as  $\geq 2$  oral steroid bursts OR hospital admissions for acute wheeze in the last 12 months, with at least one oral steroid burst OR hospital admission in the last 6 months.

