## 5. RANDOMISATION AND ENROLMENT PROCEDURE

### 5.1 Randomisation practicalities

All randomisation and enrolment will occur during routine working hours – as all research visits will take place in the Biomedical Research Unit during the week between 9am and 5pm. Children will be recruited when they are clinically well, not during an acute attack.

We will use the Imperial INFORM database Unit to undertake randomisation

We wish to stratify randomisation according to sex and age, to achieve similar numbers of boys and girls in each group, and to have a similar average age for each group.

The age stratification will be as follows: >1-  $\leq$ 3 years and >3 -  $\leq$ 5 years

As wheezing in preschool children is a seasonal disorder (majority of symptoms and exacerbations occur between September – April each year), the baseline assessments and pre-randomisation visits will be arranged between late August – December each year, so that randomisation and intervention take place between September – January each year, to allow the 4 month intervention period to fall within the main season.

All patients will be given a study specific 24hrs emergency contact card immediately after being randomised. The card includes details of the study: Study title, patient trial number, CI/PI's contact details along with out of hours contact details in case of emergency.

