**Long-term follow-up assessments:**

After the first follow-up visit at 4 months, parents of children will be contacted at 6 months by phone call to assess symptoms, unscheduled healthcare visits, courses of steroids and medication. They will also be asked to attend annually for a follow-up visit when all of the above plus lung function, exhaled nitric oxide and sputum induction will be performed. Urine samples will also be collected and stored if parents consent. These assessments will continue until the end of the trial period, or until the child reaches the age of 6 years, whichever is sooner.

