**8.6 TRIAL CLOSURE**

The minimum number of children to be recruited into each arm is 36, however, as this is a proof of concept study, an accurate power calculation cannot be performed, indeed part of the reason for this study is to determine the size of a larger trial that would be needed to definitively answer whether pathological phenotype based management is superior to current clinical guidelines. Therefore, recruitment of patients will continue until the end of the trial funding period, December 2018.

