## **9.0 STATISTICS AND DATA ANALYSIS**

Categorical data will be presented as number and percentage and comparisons between groups done using the chi squared or Fishers exact test. All numerical data will be tested for normality and normally distributed data will be presented as mean  $\pm$  SD and comparisons between groups done using the 2 sample independent t test. For the data that are not normally distributed the median (IQR) will be presented and comparisons between groups done using the Mann-Whitney test. Poisson regression will be done to determine the factors that affect the primary endpoint, the number of unplanned hospital visits.

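### Admissions and oral-steroid days are counted up to 1 year after the intervention, but only 4 months of follow-up are guaranteed and section 9.0 makes no allowance for unequal observation time

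*Combined protocol and SAP*

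**What the plan says.** **Horizon.** The Study Summary (Outcome Measures) ends its list of secondary outcomes with "number of days of oral steroids during the 4 month intervention period, and up to 1 year later". Section 3.1 lists the same outcomes without any time window.

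**Guaranteed follow-up.** Section 3 (Study duration) states: "The minimum follow-up is at the end of the 4 month intervention period, maximum follow-up will be for 3 years".

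**End of contacts.** Section 8.4 (Long-term follow-up assessments) says: "These assessments will continue until the end of the trial period, or until the child reaches the age of 6 years, whichever is sooner". The end of the trial is given no date.

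**Recruitment.** Section 8.6 says that "recruitment of patients will continue until the end of the trial funding period, December 2018". Section 5.1 confines entry to one part of the year: "randomisation and intervention take place between September – January each year".

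**Analysis.** For normally distributed numerical data, section 9.0 has "comparisons between groups done using the 2 sample independent t test". Otherwise: "For the data that are not normally distributed the median (IQR) will be presented and comparisons between groups done using the Mann-Whitney test". Its single regression is tied to the primary endpoint: "Poisson regression will be done to determine the factors that affect the primary endpoint, the number of unplanned hospital visits". Section 9.0 mentions no rate, follow-up time or censoring rule, and no subset with complete follow-up. Section 4.4 deals with withdrawal and section 8.5 with loss of contact. Neither covers a child who stays in the study but entered late.

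**The concern.** One year after a 4-month intervention is month 16 from randomisation. Because recruitment stays open until funding ends, a child who enters in the last season reaches month 16 only if follow-up runs more than a year past December 2018, and nothing in the documents says that it does. How long a child is observed then depends on the date of entry. This is separate from the sixth-birthday stop and from withdrawal, and it affects families who comply fully.

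A raw count over 4 months and a raw count over 16 months are different quantities. If they are compared together, the mean or median per child and the absolute difference between arms refer to no stated period. This matters for two reasons. Fewer oral-steroid days is part of the hypothesis in section 1.2. Informing the size of a larger trial is a stated aim, and an average taken over an unknown mix of windows cannot be used for that purpose.

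**Working it through.** The plan gives no figure of its own for follow-up, so there is none to reproduce. The check is calendar arithmetic.

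**Inputs from the documents.** Horizon 4 + 12 = 16 months; minimum follow-up 4 months; randomisation September to January; recruitment to December 2018.

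**Assumptions (not in the documents).** K = 3, 4 or 5 seasons with equal numbers in each; entry uniform within a season; last season cut at the end of December 2018; closure at the end of December 2018 (every child still given month 4) or at the end of April 2019 (when the last recruit completes month 4); constant event rate; no shortening by the age limit.

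**Closure April 2019.** Sixteen months back is the end of December 2017, so children randomised from January 2018 fall short.
- Share short = (1 + 1/5)/K = 40%, 30%, 24% for K = 3, 4, 5.
- Last-season children have 4 to 8 months (mean 6), a deficit of 10. January 2018 entrants have a mean of 15.5 months, a deficit of 0.5 in one-fifth of that season.
- Mean window = 16 - (10 + 0.1)/K = 12.6, 13.5, 14.0 months.
- Understatement = 10.1/(16K) = 21%, 16%, 13%.

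**Closure December 2018.** Children randomised from September 2017 fall short.
- Share short = 2/K = 67%, 50%, 40%.
- Last-season children have 4 months (deficit 12). The season before has 11 to 16 months (mean deficit 2.5).
- Mean window = 16 - 14.5/K = 11.2, 12.4, 13.1 months.
- Understatement = 14.5/(16K) = 30%, 23%, 18%.

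With a constant rate and rate ratio, the absolute difference between arms shrinks by the same percentage as the mean count.

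**Other readings.**
- Equal accrual per month instead of per season: 21-36% short (April 2019) or 38-64% (December 2018).
- The year counted from randomisation (month 12): 1/K = 20-33% short (April 2019) or 1.2/K = 24-40% (December 2018).

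**Power and type I error.** These come from simulation with 50 per arm and assumed gamma-Poisson counts (2 events per child-year, dispersion 0.7, true rate ratio 0.67). The two settings were 3 seasons closing April 2019 and 4 seasons closing December 2018.
- Mann-Whitney on complete 16-month counts has 38-39% power; on the truncated counts it has 27-29%. The test is the same, so this loss comes from the missing observation time.
- Type I error stays at about 5%.

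**The case against.** **The wording is an upper limit.** Up to 1 year need not promise 16 months for every child, and section 3 openly declares follow-up from 4 months to 3 years. That stands. It does not remove the problem, because declared variable follow-up is exactly what calls for an analysis that uses follow-up time.

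**Section 9.0 is generic.** A reader might infer that the plan instructs the analyst to treat a late recruit's short count as a complete one. The documents do not say so; they do not say how such children are handled. What can be said is that a raw comparison is the only method offered for these outcomes.

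**Closure and accrual are unknown.** Section 8.6 dates the end of recruitment and funding, not the end of follow-up. Also, some children counted as short under an April 2019 closure have 15 to 16 months; counting only those below 15 months gives 20-34%. The percentages are therefore a conditional range.

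**The power effect is easily overstated.** A reader might set a raw Mann-Whitney test against a negative binomial model with an offset and credit the whole gain to follow-up time. Separating the two in the same settings, at rate ratio 0.67, gives:

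| Analysis | Power |
|---|---|
| Mann-Whitney, raw counts | 27-28% |
| Mann-Whitney, rates | 28-30% |
| Negative binomial, no offset | 36% |
| Negative binomial, with offset | 39-40% |

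Most of the gain comes from the count model. The offset recovers only a few points, since it cannot restore time that was never observed. Steroid days also cluster within courses, so this simulation does not describe them well.

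**An offset over months 0-16 has its own weakness.** Late recruits contribute mainly in-season time on treatment, while others add post-treatment and summer time. In one illustrative run (effect confined to months 0-4 at rate ratio 0.5, strong assumed seasonality), the pooled offset model gave 0.77-0.80, against 0.84-0.85 with complete follow-up. This stands, and it is why the two periods should be analysed separately.

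**Conclusion.** The point holds as a gap between the outcome definition, the guaranteed follow-up and the analysis. The longer-term admissions and steroid-day counts would mix observation periods from 4 to 16 months. Under the assumed accrual and closure dates, they and their absolute difference are understated by roughly 13-30%. Some power is lost, by an amount that depends on event rates the documents do not give.

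Three stronger inferences are not supported. Neither arm is favoured, because entry dates are shared by randomisation. Type I error is not inflated. The primary outcome is not affected by the 1-year horizon, because it is confined to the 4 months that section 3 guarantees.

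This is worth correcting before analysis. It does not undermine the main comparison of a proof-of-concept study, but it makes the longer-term figures unsuitable for planning the next trial.

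**What to change.** 1. In sections 3.1 and 9.0, make admissions and oral-steroid days over the fixed 0-4 month period the main secondary comparison.
2. Define the post-intervention outcome separately, from month 4 to month 16 or last contact, whichever comes first. Require the date of last contact to be recorded; the documents schedule contacts but do not expressly say that their dates are captured.
3. Analyse this outcome as a rate, with treatment arm in the model and log follow-up time as offset: negative binomial for admissions, Poisson with robust variance for steroid days. Children with no time after month 4 cannot enter this model, and their number should be stated.
4. Report the rate ratio with 95% CI and the number of children observed at months 4, 10 and 16, by arm. Add a sensitivity analysis in children with the full 16 months.
5. In section 3, state that the 4-month minimum covers the primary and main secondary comparisons and that later outcomes have variable follow-up.

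**Cost.** Wording, one recorded date and a modest amount of analysis; no extra children or visits. The rate model assumes a roughly constant rate and effect over follow-up, whereas season and time since treatment vary with entry date. The post-intervention result should therefore be labelled supportive only.
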